9.3.2. Hormone Panel

At all study visits (including screening) except Week 8 and Week 10, a blood sample should be collected for hormone measurements in the morning approximately 2 to 3 hours after the morning glucocorticoid dose (and fludrocortisone dose if taking) is taken. Additional blood samples for hormone measurements may be collected at unscheduled visits if clinically indicated.

In addition, a predose blood sample for hormone measurements prior to the morning glucocorticoid dose (and fludrocortisone dose if taking) will be collected at Day 1 (baseline),

Weeks 4 and 24, and Months 12, 13 (for subjects re-randomized at Month 12), 18, 24, and every 12 months thereafter. At these visits, subjects will hold their morning glucocorticoid dose until arriving at the study site so that a blood sample for hormone measurements can be collected. Subjects will then take their morning dose of glucocorticoid (and fludrocortisone dose if taking) at the study site, with another blood sample collected approximately 2 hours later. The second (2-hr postdose) blood sample should be collected prior to 1100 hours. Subjects not on a morning glucocorticoid should still have 2 morning blood samples taken (eg, with the glucose tolerance test at Day 1, Week 24, Month 12, etc.; and/or before and 2 hours after the morning study drug dose). Additional plasma or serum hormone levels may be evaluated using the second blood sample collected at these timepoints.

The hormone panel will include assessment of:

- Adrenal androgens and precursors (ACTH, 17-OHP, cortisol, androstenedione, testosterone) and sex hormone binding globulin (only for the second blood sample collected at Day 1, Weeks 4 and 24, and Months 12, 13, 18, 24, and every 12 months thereafter)
- Reproductive function (luteinizing hormone [LH], FSH, progesterone)
- Mineralocorticoid status (upright PRA)

The blood samples will be processed and stored according to the procedure as specified in the laboratory manual.

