**Table 3: Hormone Reference Ranges**

Hormone Reference Ranges	
Lab Analyte	Reference Ranges: conventional units; SI units
Androstenedione (conversion factor from ng/dL to nmol/L: x 0.0349)	
Adult Male:
 
18-30 years: 50-220 ng/dL; 1.745 - 7.678 nmol/L
 
31-50 years: 40-190 ng/dL; 1.396 - 6.631 nmol/L
 
51-60 years: 50-220 ng/dL; 1.745 - 7.678 nmol/L
 
Adult Female:
 
Mid Follicular: 51-213 ng/dL; 1.7799 - 7.4337 nmol/L
 
Surge: 73-230 ng/dL; 2.5477 - 8.027 nmol/L
 
Mid Luteal: 73-184 ng/dL; 2.5477 - 6.4216 nmol/L
 
Postmenopausal: 20-75 ng/dL; 0.698 - 2.6175 nmol/L

17-OH Progesterone (17-OHP) (conversion factor from ng/dL to nmol/L: x 0.0303)	
Adult Male:
 
18-30 years: 32-307 ng/dL; 0.9696 - 9.3021 nmol/L
 
31-40 years: 42-196 ng/dL; 1.2726- 5.9388 nmol/L
 
41-50 years: 33-195 ng/dL; 0.9999 - 5.9085 nmol/L
 
51-60 years: 37-129 ng/dL; 1.1211 - 3.9087 nmol/L
 
>= 61 years: Not established
 
Adult Females:
 
Pre-menopausal mid follicular: 23-102 ng/dL; 0.6969 - 3.0906 nmol/L
 
Pre-menopausal surge: 67-349 ng/dL; 2.0301-10.5747 nmol/L
 
Pre-menopausal mid luteal: 139-431 ng/dL; 4.2117 - 13.0593 nmol/L
 
Post-menopausal phase: <=45 ng/dL; 1.3635 nmol/L

Progesterone (conversion factor from ng/mL to nmol/L: x 3.18)	Male: <0.15ng/mL; 0.477 nmol/L, <0.48 nmol/L; 1.5264 nmol/L  Female: Premenopausal, not pregnant: <23.90 ng/mL, <76 nmol/L Female, pregnant: 11.00 – 214 ng/mL, 34.98 - 680.52 nmol/L Female, postmenopausal: <0.13 ng/mL, <0.41 nmol/L
ACTH (conversion factor from pg/mL to pmol/L: x 0.22)	Males and Females: 7.2 – 63.3 pg/mL; 1.584 -13.926 pmol/L
Follicle stimulating hormone (FSH) (conversion factor from mIU/mL to IU/L: x 1.0)	Male: 1.6 - 11.0 mIU/mL (IU/L) Female: 1.8 - 20.4 mIU/mL (IU/L)
Luteinizing Hormone (LH) (conversion factor from mIU/mL to IU/L: x 1.0)	Male: 1.7 - 8.6 mIU/mL (IU/L) Female: 1.0 - 95.6 mIU/mL (IU/L)
Sex Hormone Binding Globulin (SHBG)	Male: 10.0 - 80.0 nmol/L (same in SI) Female: 20.0 - 130.0 nmol/L (same in SI)
Total Testosterone (Medpace/MRL) (conversion factor from ng/mL to nmol/L: x 3.47)	Male: 2.70- 10.70 ng/mL; 9.37-37.13 nmol/L Female: 0.06 - 0.86 ng/mL; 0.21-2.98 nmol/L
Total Testosterone (Quest) (conversion factor from ng/dL to nmol/L: x 0.0347)	Male: 250 - 1100 ng/dL; 8.675 - 38.17 nmol/L Female: 2 - 45 ng/dL; .0694 - 1.5615 nmol/L

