## **9.6. Exploratory Efficacy Endpoints**

The following sections describe the exploratory efficacy endpoints and methods of summarization and analysis. For all analyses of the exploratory efficacy endpoints, missing data

will not be imputed and only observed cases will be used. All p-values produced from the analyses in this section will be considered nominal p-values and will not be adjusted for multiplicity.

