### **9.6.1. Hormone Measurements**

ACTH, total testosterone, follicle stimulating hormone (FSH), luteinizing hormone (LH), sex hormone binding globulin (SHBG), and progesterone will be summarized with descriptive statistics by visit and treatment group. Note that for hormone parameters that were collected both pre- and post-GC dose, the following summaries will be produced for both pre-GC dose and post-GC dose values. Both observed and change from baseline values will be displayed. All summaries of testosterone and progesterone will be stratified by sex. Summaries of FSH, LH, and SHBG will also be stratified by sex as well as by combined sexes. The change from baseline to Week 24 for each of these parameters will be analyzed using an ANCOVA model as described in Section 9.2.1. Descriptive statistics and LS means for change from baseline to Week 24 in each of these hormone parameters will be presented by treatment group along with the LS-mean treatment difference, 95% confidence intervals, and p-value.

Shifts from baseline to Week 4 in gonadotropin values (LH and FSH) will be presented in tables by sex as well as by combined sexes. Postmenopausal women will be excluded from the shift tables. Each shift table will have four rows and four columns, with rows reflecting the reference range category at baseline (low, normal, high, missing), and columns reflecting the reference range category at Week 4 (low, normal, high, missing). A “Total” row and “Total” column will also be included. The number and percentage of subjects in each shift category will be displayed in the table; percentages will be based on the number of subjects included in the table.

The achievement of response at Week 24 (as defined for each of the following responder analyses described below) will be analyzed using a CMH test as described in Section 9.2.2. The CMH test will compare treatment groups and will include stratification factors (with the exception of sex) used in the randomization. Subjects who are missing Week 24 data will be omitted from the analysis.

A responder definition for the normalization of LH will be defined as subjects with abnormal LH levels at baseline (defined as < LLN or > ULN) and achieve normalization at Week 24 in male subjects (based on pre-GC dose LH levels). The number and percentage of subjects meeting this responder definition at Week 24 will be summarized by treatment group. This responder definition and summarization will also be repeated for FSH.

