A responder definition for the normalization of testosterone in female subjects will be defined as female subjects with testosterone levels that are greater than or equal to 1.2x ULN (based on age) at baseline and decrease to within the normal range at Week 24 based on the average of the pre-glucocorticoid and post-glucocorticoid testosterone levels at the applicable visit. The number and percentage of female subjects meeting this responder definition at Week 24 will be summarized by treatment group.

A responder definition for the normalization of progesterone in female subjects of child-bearing potential not on hormonal contraceptives will be defined as female subjects with a progesterone level >0.6 ng/mL at baseline and decrease to a progesterone level <0.6 ng/mL at any point during the DB period of the study. The average of the progesterone levels will be used at visits where more than one hormone sample is collected. This analysis will be restricted to female subjects

who are of childbearing potential and are not on hormonal contraceptives. The number and percentage of female subjects in this subset meeting this responder definition at each visit in the DB period will be summarized by treatment group.

A responder definition for the ratio of androstenedione to testosterone (A4/T) in male subjects will be defined as male subjects who have A4/T greater than or equal to 0.5 (based on the pre-glucocorticoid dose values for androstenedione and testosterone) at baseline and who achieve A4/T less than 0.5 at Week 24. The number and percentage of male subjects meeting this responder definition at Week 24 will be summarized by treatment group.

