A responder definition for the normalization of progesterone in female subjects of child-bearing potential not on hormonal contraceptives will be defined as female subjects with a progesterone level  $>0.6$  ng/mL at OL baseline and decrease to a progesterone level  $<0.6$  ng/mL at any postbaseline visit thereafter. The average of the progesterone levels will be used at visits where more than one hormone sample is collected. This analysis will be restricted to female subjects who are of childbearing potential and are not on hormonal contraceptives. Descriptive statistics will be presented by treatment group for the number and percentage of female subjects classified as responders and non-responders at OL baseline and each visit thereafter in the OL period.

A responder definition for the normalization of LH will be defined as subjects with abnormal LH levels at OL baseline (defined as  $<$  LLN or  $>$  ULN) and achieve normalization at Month 12 in male subjects based on pre-GC dose levels. The number and percentage of subjects meeting this responder definition at Month 12 will be summarized by treatment group. This responder definition and summarization will also be repeated for FSH.

A responder definition for the ratio of androstenedione to testosterone (A4/T) in male subjects will be defined as male subjects who have A4/T greater than or equal to 0.5 (based on the pre-glucocorticoid dose values for androstenedione and testosterone) at OL baseline and who achieve A4/T less than 0.5 at any postbaseline visit thereafter. Descriptive statistics will be presented by treatment group for the number and percentage of male subjects classified as responders and non-responders at OL baseline and each visit thereafter in the OL period.

In addition to the serum hormone measurement summaries described above, urine androgen metabolite levels, including androsterone and etiocholanolone (corrected for urine creatinine), will be summarized with descriptive statistics by visit and treatment group. Summary tables will include observed and change from OL baseline values for each urine androgen parameter.

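### The any-visit progesterone responder in SAP 9.6.1 is confounded by menstrual cycle phase and does not match its own Week 24 test

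*SAP*

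**What the plan says.** SAP 9.6.1 defines the responder as a woman with progesterone above 0.6 ng/mL at baseline and a later "decrease to a progesterone level <0.6 ng/mL at any point during the DB period of the study". The analysis is limited to women "who are of childbearing potential and are not on hormonal contraceptives". Where a visit has two samples, they are averaged.

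The section gives two other timings for the same endpoint. The paragraph on testing says: "The achievement of response at Week 24 (as defined for each of the following responder analyses described below) will be analyzed using a CMH test". The display instruction says that women "meeting this responder definition at each visit in the DB period will be summarized by treatment group".

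On sampling, Protocol 9.3.2 states: "At all study visits (including screening) except Week 8 and Week 10, a blood sample should be collected for hormone measurements". Collection is fixed relative to the morning glucocorticoid dose; nothing ties it to cycle phase. SAP Table 3 gives one progesterone range for non-pregnant premenopausal women, "Premenopausal, not pregnant: <23.90 ng/mL, <76 nmol/L", although it splits androstenedione and 17-OHP by phase.

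SAP 10.2 carries the rule into the open-label period, with response "at any postbaseline visit thereafter. The average of the progesterone levels will be used at visits where more than one hormone sample is collected". SAP 9.6 sets the inferential status: "All p-values produced from the analyses in this section will be considered nominal p-values".

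**The concern.** A single baseline value above 0.6 ng/mL can arise in two ways. One is persistent progesterone of adrenal origin, which the endpoint is meant to capture. The other is an ordinary luteal phase on Day 1. The upper limit in Table 3 is about 40 times the cut-off (23.90 / 0.6 = 39.8), so a value above 0.6 can lie well inside the plan's own normal range.

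With eight later samples at arbitrary points of the cycle, a woman of the second kind is likely to be sampled at least once outside her luteal phase. She is then counted as normalised in whichever arm she was assigned. Such women add responses to both arms, pull the comparison toward no difference, and make the reported normalisation rate hard to read as a treatment effect.

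Separately, three timings for one endpoint leave the programmer to choose what enters the CMH test.

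**Working it through.** The documents state no expected rate, sample size or power for this endpoint, so there is no figure of the plan's own to reproduce. The one related figure agrees: SAP 9.5.5 takes regular cycles as 21 to 35 days and expects about 4 to 8 over the period; 168/35 = 4.8 and 168/21 = 8.0.

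**Inputs from the documents**
- Eight post-baseline samples: Weeks 2, 4, 6, 9, 12, 16, 20 and 24, target days 14, 28, 42, 63, 84, 112, 140 and 168 (SAP Table 4).
- Visit windows: +5 days through Week 12, ±5 days after (Protocol Table 1, footnote a).
- Cycle length 21 to 35 days (SAP 9.5.5).

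**Assumptions not in the documents**
- Progesterone exceeds 0.6 ng/mL only in the last h days of each cycle; h = 14, varied from 10 to 16.
- Day 1 is uniformly distributed over the luteal phase; no drug effect.
- Within-woman cycle SD of 2 days.

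**Hand check: exact 28-day cycles, h = 14, visits on target**
Let R be the days from Day 1 to next menses, uniform on (0, 14). A later sample is low if more than 14 days remain to the following menses.
- Week 2 is 13 days after Day 1. If R < 13, the days remaining are R + 28 − 13 = R + 15 > 14, so the sample is low. Probability 13/14 = 93%.
- Week 4 is 27 days after Day 1. The days remaining are R + 1, which exceeds 14 when R > 13. This catches the other 1/14.
- The any-visit rate therefore reaches 100% by Week 4.
- Week 24 is 167 days after Day 1. The days remaining are R + 168 − 167 = R + 1, so the sample is low with probability 1/14 = 7%.

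**Simulation: 100,000 women per setting, cycle variation and visit windows included**

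| Setting | Any visit | Week 24 only |
|---|---|---|
| Cycles 21–35 days, h = 14 | 99.7% | 47% |
| Cycles 21–35 days, h = 10 | 100% | 62% |
| Cycles 21–35 days, h = 16 | 98.3% | 39% |
| 21-day cycles, h = 14 | 98.1% | 30% |
| 28-day cycles, h = 14 | 100% | 33% |

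In the first row, Week 2 alone gives 79%.

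The Week 24 rate depends on how the cycle length fits the visit day. It is about 0 to 60% for 28-day and mixed cycles, but 93% for exact 30-day cycles on target days: 167 = 5 × 30 + 17, so the days remaining are R + 13, which exceeds 14 with probability 13/14.

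**Relaxing the follicular assumption** (first row, each follicular sample below 0.6 with probability q)

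| q | Any visit |
|---|---|
| 0.9 | 99.1% |
| 0.7 | 96.6% |
| 0.5 | 90.0% |
| 0.3 | 72.9% |
| 0.1 | 34.3% |

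**A second weakness of the any-visit rule, apart from cycling**
A woman with persistently raised progesterone and an assumed chance p per visit of dipping below 0.6 responds with probability 1 − (1 − p)^8. This is 34% at p = 0.05 and 57% at p = 0.10, with no drug effect.

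**Open-label period**
The target days for Months 7, 8, 9, 10 and 12 are 28, 56, 84, 112 and 168 days after Week 24. All are multiples of 28. The no-effect response in women luteal at Week 24 was 56 to 96% under the cycle assumptions tried, but by this arithmetic it is zero for exact 28-day cycles on target. The rate again reflects cycle length.

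**The case against.** A reader might infer that nearly every woman with a luteal Day 1 responds in either arm whatever the drug does, so that the endpoint carries no information. The documents do not support that, for four reasons.

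- The near-100% figure needs follicular progesterone below 0.6 ng/mL, which the documents do not give. Protocol 5.1 describes progestogen overproduction in this disease, and exclusion criterion 3 removes women whose pre-dose 17-OHP is below the upper limit. The assumption is therefore doubtful for some enrolled women. A drug effect could show in exactly those women.
- The figure covers only ovulating women who are luteal on Day 1. Their number is unknown, so the dilution of the whole comparison cannot be quantified.
- It holds under one of three timings. Read at Week 24, as the test paragraph says, the no-effect rate is generally far lower.
- The consequence is small. The p-value is nominal, and the open-label version is descriptive. SAP 4.4 lists change in progesterone, not this responder, as the exploratory endpoint, and an ANCOVA of that change is planned.

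All four stand as limits on size. None removes the flaw. With only half of follicular samples below 0.6, 90% of these women still respond without a drug effect, and a Week 24 reading is still driven by cycle phase. The conflict between the timings needs no physiological assumption at all.

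**Conclusion.** The point holds in limited form. As written, the progesterone responder can count ordinary cycling as normalisation, and its any-visit definition disagrees with both the Week 24 test and the by-visit table. Under the stated assumption of 10 to 14 luteal days and low follicular values, 98 to 100% of ovulating women with a luteal Day 1 qualify without a drug effect. The rate falls to about 34% if follicular samples are rarely below the cut-off. The likely direction is dilution toward no difference. The impact is confined to one exploratory analysis and its descriptive open-label counterpart; no primary, key secondary or secondary conclusion is affected.

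**What to change.** **SAP 9.6.1**
- Define baseline elevation as post-dose progesterone above 0.6 ng/mL at Screening Visit 1, Screening Visit 2 and Day 1. All three samples are already collected, the two screening visits about 2 weeks apart. In simulation this leaves about 0 to 7% of normally cycling luteal-Day-1 women in the denominator when visits stay near 2-week spacing, and 9 to 21% if screening is stretched; short cycles fare worst.
- Use post-dose values at every visit. Only Day 1 and Weeks 4 and 24 have a pre-dose sample, so the present averaging compares unlike quantities.
- Replace the any-visit rule with one rule that matches the CMH test, for example response at Week 24, with by-visit rates descriptive. Keeping the any-visit rule after tightening the baseline is not enough, because of the any-of-eight effect shown above.
- Use the menstrual eDiary (Protocol 9.3.7) to flag the cycle phase of each sample where available. IUD users do not keep this diary, so some women will remain unclassified.

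**SAP 10.2**
- Do not try to exclude cycling with Weeks 12, 16, 20 and 24. They are multiples of 28 days apart, so a woman with exact 28-day cycles who is luteal at one is luteal at all four.
- Carry forward the three-sample pre-treatment elevation, or use diary phase. Label the rates descriptive and confounded by cycle phase.

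**Cost:** SAP wording only and no new samples. The price is a smaller denominator in an exploratory analysis. Under SAP 6.1, a change made after the Week 24 database lock would be post hoc and should be labelled so.

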#### **9.6.2. Urine Androgen Metabolite Levels**

Urine androgen metabolite levels, including androsterone and etiocholanolone (corrected for urine creatinine), will be summarized with descriptive statistics by visit and treatment group. Summary tables will include observed and change from baseline values for each urine androgen parameter. The change from baseline to Week 24 for each of these parameters will be analyzed using an ANCOVA model as described in Section 9.2.1. Descriptive statistics and LS means for change from baseline to Week 24 each of these parameters will be presented by treatment group along with the LS-mean treatment difference, 95% confidence intervals, and p-value.

#### **9.6.3. Metabolic Assessments**

In addition to HOMA-IR and glucose tolerance, other metabolic assessments include a fasting lipid panel (with total cholesterol, low-density lipoprotein [LDL], and high-density lipoprotein [HDL], triglyceride) as well as glycated hemoglobin (HbA1c) (stratified by subjects with or without diabetes mellitus). These metabolic parameters will be summarized with descriptive statistics by visit and treatment group. Summary tables will include observed and change from baseline values for each lab parameter. The change from baseline to Week 24 for each of these parameters will be analyzed using an ANCOVA model as described in Section 9.2.1. Descriptive statistics and LS means for change from baseline to Week 24 each of these parameters will be presented by treatment group along with the LS-mean treatment difference, 95% confidence intervals, and p-value.

#### **9.6.4. Bone Mineral Density**

BMD (assessed via DXA) will be summarized with descriptive statistics by visit and treatment group. Summary tables will include observed and change from baseline values for BMD (in g/cm^2) for each region of measurement.

The number and percentage of subjects meeting criteria for normal BMD (T-score  $\geq$  -1.0), osteopenia (T-score  $< -1.0$  to  $> -2.5$ ), or osteoporosis (T-score  $\leq -2.5$ ) will be summarized by visit and treatment group. Descriptive statistics for observed and change from baseline in BMD T-scores will also be summarized by treatment group by visit and region of measurement.

In addition to this, the change from baseline to Week 24 in bone mineral density (for both g/cm^2 and T-score) will be analyzed using an ANCOVA model as described in Section 9.2.1.

Descriptive statistics and LS means for change from baseline to Week 24 in BMD (for both g/cm^2 and T-score) will be presented by treatment group along with the LS-mean treatment difference, 95% confidence intervals, and p-value.

### **9.6.5. Body Composition (excluding fat mass)**

Total lean body mass and total body mass (assessed via DXA) will be summarized with descriptive statistics by visit and treatment group. The summary table will include observed, change from baseline, and percent change from baseline values. The change from baseline to Week 24 for total lean mass and total body mass will each be analyzed using an ANCOVA model as described in Section 9.2.1. Descriptive statistics and LS means for change from baseline to Week 24 for total lean body mass and total body mass will be presented by treatment group along with the LS-mean treatment difference, 95% confidence intervals, and p-value.

Descriptive statistics for the total body mass (including the individual components of fat mass and lean mass) may also be displayed graphically by treatment group.

### **9.6.6. Hirsutism**

Visual analog scales (VAS) were used to assess the subject's perception of severity of hirsutism in all female subjects, scored on a 100 mm visual analog scale, from 0 mm (no symptoms) to 100 mm (very severe symptoms). Observed and change from baseline values in VAS scores for hirsutism will be summarized descriptively by visit and treatment group. Mean ( $\pm$ SEM) observed values at each visit will be summarized in line graphs by treatment group. Similar graphs will be presented for the change from baseline values.

The change from baseline to Week 24 in VAS score for hirsutism will be analyzed using an ANCOVA model as described in Section 9.2.1 (with the exception of sex as a stratification factor). Descriptive statistics and LS means for change from baseline to Week 24 in the VAS score for hirsutism will be presented by treatment group along with the LS-mean treatment difference, 95% confidence intervals, and p-value.

